2.4.8 Further anti-neoplastic therapy

Anti-neoplastic therapy regimen received between EOT and progression will also be collected as well as the first regimen received after progression. Additionally, the tumortumor response classification was described in Table 14-5 of the protocol after the start of anti-neoplastic drugs. For details on the censoring rules, see [Appendix 1 of the study protocol].

Clinical review of study data will be performed to identify anti-neoplastic medications that are not allowed during study treatment.

Anti-neoplastic therapies since discontinuation of study drug will be listed and summarized by ATC class, preferred term and treatment arm by means of frequency counts and percentages in separate summaries using the Full Analysis Set.

2.5 Analysis of the primary objective

The primary objective in this study is to assess PFS based on investigator's assessment on the combination treatment of everolimus + exemestane and placebo + exemestane in Chinese postmenopausal women with estrogen receptor positive, HER2-negative, locally advanced, recurrent, or metastatic breast cancer after recurrence or progression on prior letrozole or anastrozole. The primary analysis for efficacy was conducted when approximately 110 PFS events have been documented, the corresponding results for the PFS are provided in the primary CSR [Study Y2202-Section 11.1] (DCO: 19 May-2020).

2.5.1 Primary endpoint

Progression-free survival (PFS) derived from an investigator's assessment of radiology data will be used as the primary efficacy variable. Disease progression for primary efficacy endpoint derivation will be assessed using the local (treating center's radiologist's) investigator's tumor assessment per RECIST 1.1.

The PFS is defined as the time from the date of randomization to the date of the first documented disease progression or death due to any cause, whichever occurs first. If a subject has not progressed or died at the analysis cut-off date, or if she receives any further anti-cancer therapy, PFS will be censored at the time of the last adequate tumor assessment before the cut-off date or the anti-cancer therapy date, whichever occurs first. Disease progression for primary efficacy endpoint derivation will be assessed using the local (treating center's radiologist's) investigator's tumor assessment. Definitions and further details on PFS can be found in Appendix 1 of the protocol.

Discontinuation due to disease progression (collected on the "End of treatment" and "End of Post Treatment Disposition eCRF page" page) without supporting objective evidence satisfying progression criteria per RECIST 1.1 will not be considered a progressive disease.

Data included in efficacy analyses

The final analysis for safety and efficacy will be conducted closeout at the end of the study. Efficacy analyses will include all data observed in subjects from the FAS regardless of whether the data were observed on-treatment or after the study treatment discontinuation until the analysis cut-off date. In particular, the "30 days" rule applied to all safety analyses will NOT be used for efficacy analyses.

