#### 14.1.3.1 Best overall response

The best overall response is the best response recorded from the start of the treatment until disease progression/recurrence (taking as reference for PD the smallest measurements recorded since the treatment started). In general, the patient's best response assignment will depend on the achievement of both measurement and confirmation criteria.

The best overall response will usually be determined from response assessments undertaken while on treatment. However, if any assessments occur after treatment withdrawal the protocol should specifically describe if these will be included in the determination of best overall response and/or whether these additional assessments will be required for sensitivity or supportive analyses. As a default, any assessments taken more than 30 days after the last dose of study treatment will not be included in the best overall response derivation. If any alternative cancer therapy is taken while on study any subsequent assessments would ordinarily be excluded from the best overall response determination. If response assessments taken after withdrawal from study treatment and/or alternative therapy are to be included in the main endpoint determination, then this should be described and justified in the protocol.

Where a study requires confirmation of response (PR or CR), changes in tumor measurements must be confirmed by repeat assessments that should be performed not less than 4 weeks after the criteria for response are first met.

Longer intervals may also be appropriate. However, this must be clearly stated in the protocol. The main goal of confirmation of objective response is to avoid overestimating the response rate observed. In cases where confirmation of response is not feasible, it should be made clear when reporting the outcome of such studies that the responses are not confirmed.

- For non-randomized trials where response is the primary endpoint, confirmation is needed.
- For trials intended to support accelerated approval, confirmation is needed
- For all other trials, confirmation of response may be considered optional.

The best overall response for each patient is determined from the sequence of overall (lesion) responses according to the following rules:

- CR = at least two determinations of CR at least 4 weeks apart before progression where confirmation required or one determination of CR prior to progression where confirmation not required

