Clinical benefit rate (CBR) is defined as the proportion of subjects with best overall response of CR, PR, or overall lesion response of stable disease (SD for measurable disease and non-CR/non-PD (NCRNPD) for non-measurable disease) with duration of 24 weeks or longer. A subject will be considered to have a SD/NCRNPD for 24 weeks or longer if SD/NCRNPD is recorded at 24 weeks or later after randomization. Taking into account the allowed time window for tumor assessment visits, the SD/NCRNPD response has to be recorded at 23 weeks or later after randomization to be included in the CBR calculation. Best overall response of CR, PR and overall lesion response of SD/NCRNPD are defined according to RECIST 1.1 (see Appendix 1). CBR will be calculated based on the FAS according to the ITT principle, using local radiologist's/investigator's tumor assessment. Subjects with non-measurable disease only at baseline will be included in the numerator if they achieve a complete response.

Time to response (TTR)

Time to overall response (TTR) of CR or PR is defined as the time from randomization to first documented response (CR or PR, which must be confirmed subsequently) for subjects with a confirmed CR or PR. It will be summarized using local radiologist's/investigator's tumor assessment.

Duration of Response (DOR)

Among subjects with a confirmed response (PR or CR) per RECIST 1.1 by investigator, DOR is defined as the time from first documented response (PR or CR) to the date of first documented disease progression or death due to any cause. It will be summarized using local radiologist's/investigator's tumor assessment.

ECOG performance status

ECOG performance status (PS) scale will be used to assess physical health of subjects, ranging from 0 (most active) to 5 (least active) given in [Table 2.2](#).

ECOG PS will be evaluated at the following visits:

- Baseline (\leq 7 days prior to administration of the study drugs)
- Cycle 1 Day 1 (prior to administration of the study drugs)
- Every 2 Cycles after Cycle 1 Day 1(Cycle 3 Day 1, Cycle 5 Day 1 and etc)
- End of treatment

Table 2-2 ECOG Performance Status Scale

Score	Description
0	Fully active, able to carry on all pre-disease performance without restriction
1	Restricted in physically strenuous activity but ambulatory and able to carry out work of a light or sedentary nature, e.g., light house work, office work

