2.9 Interim analysis

Not applicable.

3 Sample size calculation

Refer to CRAD001Y2202 SAP Addendum 1 for details.

4 Change to protocol specified analyses

No change from protocol specified analysis was made.

5 Appendix

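### SAP 2.5.1 and protocol Appendix 1 set different data windows for best overall response, so ORR and CBR could count scans taken on a later anticancer therapy

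*SAP*

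**What the plan says.** **SAP 2.5.1**, in its paragraph on the data included in efficacy analyses, uses everything observed in the full analysis set "regardless of whether the data were observed on-treatment or after the study treatment discontinuation until the analysis cut-off date". It adds that the 30-day "rule applied to all safety analyses will NOT be used for efficacy analyses". New therapy appears in that section only for PFS: "or if she receives any further anti-cancer therapy, PFS will be censored at the time of the last adequate tumor assessment".

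**SAP 2.7** defines ORR as the proportion with a best overall response of CR or PR, citing Appendix 1 of the protocol, and also points to Appendix 1 for CBR. For stable disease (or non-CR/non-PD in non-measurable disease) it sets a timing condition only: "the SD/NCRNPD response has to be recorded at 23 weeks or later after randomization to be included in the CBR calculation".

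**Protocol 14.1.3.1 (Appendix 1)** sets two limits on best overall response. On late scans, the default is that "any assessments taken more than 30 days after the last dose of study treatment will not be included in the best overall response derivation". On new therapy: "If any alternative cancer therapy is taken while on study any subsequent assessments would ordinarily be excluded from the best overall response determination". A study that wants such scans in its main endpoint is told to describe and justify this in the protocol. Protocol 10.5.1.1 (ORR) and 10.5.1.3 (CBR) contain no such text.

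**SAP section 4** states: "No change from protocol specified analysis was made".

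**The concern.** The SAP carries two instructions on which scans feed best overall response. The general paragraph in 2.5.1 admits every scan after treatment stops. The definitions in 2.7 import an appendix that leaves some of those scans out. Nothing says which prevails, and section 4 implies there is nothing to settle.

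The scans in question will exist. Protocol 4.1 and 7.1.6.2 continue tumour assessment after a stop without progression. Starting a new drug is not among the reasons to end it, and regimens given between end of treatment and progression are collected. SAP 2.7 summarises ORR, CBR, time to response and duration of response again for the final report, so the choice still matters.

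At stake is whether a response or disease stabilisation seen on a subsequent drug is attributed to the randomised arm. If it is, ORR and CBR follow a different rule from PFS, which is censored for the same patient at the last adequate scan before the switch (SAP 2.5.1 and 2.5.3).

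**Working it through.** No figure in the plan depends on this point. The plan's only design calculation (protocol 10.6) concerns PFS. It reproduces as exp(ln 0.62 ± 1.645 × 2/√110) = 0.453 to 0.848, matching the stated 0.45 to 0.85, and is untouched by what follows.

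**Step 1: apply both texts to three constructed patients.** Each stops study treatment at week 10 without progression. Scans fall every 8 weeks (weeks 16 and 24).

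| Patient | SAP 2.5.1 read literally | Appendix 1 |
|---|---|---|
| A. No new drug; PR at week 16, which is 6 weeks = 42 days after last dose | Counts for ORR and CBR | Excluded by the 30-day default |
| B. New drug at week 12; PR at week 24, 14 weeks = 98 days after last dose | Counts for ORR and CBR; for time to response only if later confirmed | Excluded by the 30-day default and ordinarily by the new-therapy rule |
| C. New drug at week 12; SD at week 24 | Counts for CBR (week 23 or later) | Not literally covered |

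Patient A shows a plain conflict, but no next drug is credited. Patient B shows a conflict in which one is. Patient C falls in a gap: Appendix 1 builds the SD part of CBR on overall lesion response, while its two exclusions are written for best overall response. Neither document states a no-new-therapy condition there.

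**Step 2: look for a rule elsewhere that settles it.**
- SAP 2.7.3 carries the principles of 2.5.3 to the secondary endpoints. Section 2.5.3 gives PFS censoring dates, and no text says how censoring applies to a proportion.
- SAP 2.4.8 refers response after new antineoplastic drugs to protocol Table 14-5. That table concerns PFS, time to progression and duration of response, not best overall response. The option SAP 2.5.2 lists, F(1), ignores the new therapy, although the prose of 2.5.2 censors at it.
- Appendix 1 (14.1.3.2.10) exempts certain palliative radiotherapy from being treated as cancer therapy for best overall response and PFS. The exemption presupposes that other new therapy does affect best overall response.
- Appendix 1 ends best overall response at progression, so only patients who switch before documented progression matter.

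**Step 3: size.** Inputs: about 160 patients at 1:1 (protocol 10.6), so 80 per arm; reference rates from the earlier phase III trial (protocol 1.1.2), ORR 12.6% vs 1.7% and CBR 51.3% vs 26.4%. One patient moves an arm by 1/80 = 1.25 points. Exact (Clopper-Pearson) 90% limits are the 5% point of Beta(x, n − x + 1) and the 95% point of Beta(x + 1, n − x).

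| Illustration | Without | One patient added |
|---|---|---|
| ORR, everolimus | 10/80 = 12.5% (6.9 to 20.3) | 11/80 = 13.75% (7.9 to 21.7) |
| ORR, placebo | 1/80 = 1.25% (0.1 to 5.8) | 2/80 = 2.5% (0.4 to 7.7) |
| CBR, everolimus | 41/80 = 51.25% (41.5 to 60.9) | 42/80 = 52.5% (42.7 to 62.1) |
| CBR, placebo | 21/80 = 26.25% (18.3 to 35.6) | 22/80 = 27.5% (19.4 to 36.9) |

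The number affected is not in the documents. Assuming 0 to 5 per arm, the shift is 0 to 6.25 points (5 × 1.25).

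**The case against.** The best defence is that the specific definition governs the general paragraph. SAP 2.5.1 speaks of data after treatment discontinuation and never says that scans on a new drug count. The 30-day rule it names is the safety window. ORR and CBR are defined by reference to Appendix 1, and 2.7.3 signals an intention to use the last adequate scan before new therapy. On that reading the Appendix 1 exclusions hold and no next-drug response is credited.

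That reading is available, and it rules out the stronger claim a reader might infer: that the SAP will count responses to the next drug. The Appendix 1 limits are also a default and an ordinary practice, not absolute bars. Even so, the reading is not secured. All post-discontinuation data in 2.5.1 literally includes scans beyond 30 days, 2.4.8 points to a table whose listed option ignores new therapy, and the SD part of CBR stays uncovered either way.

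A reader might also infer a bias towards everolimus, because its toxicity causes more stops without progression. The documents do not establish this. Protocol 6.1.4 lets a patient who stops one component continue the other, so stopping everolimus need not end study treatment or lead to a new drug. SAP 2.5.1 does not count undocumented progression as progression, and such patients may switch early, possibly more often in the control arm. No rates of discontinuation or switching before progression are given for this trial.

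The effect is limited further. A PR on the next drug still needs a fall of at least 30% from study baseline before any progression, and time to response needs confirmation.

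**Conclusion.** The point stands as an unresolved conflict over the data window for best overall response, plus a gap for the SD component of CBR. The 30-day conflict is the clearest part but by itself credits no other drug. The new-therapy part could do so for ORR, CBR and, where confirmed, time to response and entry to duration of response, depending on which text is programmed.

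The size is 1.25 points per reclassified patient in an arm of 80. One patient is small against the width of an exact 90% interval (13.4 points at 10/80), but would double a control ORR of 1/80. The count per arm is an assumption and the direction is unknown. ORR, CBR and time to response are secondary and estimated without testing, and the primary PFS hazard ratio is not affected. The change should be made because it is cheap and removes an avoidable ambiguity.

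**What to change.** 1. In SAP 2.5.1 and 2.7, state that best overall response, ORR, CBR (including SD or non-CR/non-PD at 23 weeks or later), time to response and entry to duration of response use only assessments before the earlier of progression and the start of new anticancer therapy. Exempt palliative radiotherapy as Appendix 1 does.
2. Align SAP 2.4.8 and 2.7.3 with that rule, so that neither sends response classification to PFS-type censoring or to Table 14-5.
3. Choose one treatment of scans more than 30 days after the last dose with no new therapy. Either apply the Appendix 1 default to best overall response, or keep those scans, list the departure with its reason in SAP section 4, and show ORR and CBR under the 30-day default as supportive.

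The cost is a few sentences and one derivation flag, using the therapy start date already needed for PFS censoring. ORR or CBR may come out slightly lower.

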2.5.2 Statistical hypothesis, model, and method of analysis

No hypothesis testing will be performed and the primary objective of this study is to estimate hazard ratio of everolimus in combination with exemestane compared to placebo plus exemestane.

The final analysis of PFS will be based on data from investigator/local radiology review. The analysis will be performed on the FAS following the intention-to-treat (ITT) principle, i.e., subjects will be analyzed according to the treatment group they were randomized and the stratum they were assigned to at baseline. The analysis will use the default censoring and event date definitions from Table 14-5 of Appendix 1 of the study protocol, i.e. A(1), B(1), C1(1), C2(1), D(1), E(1), and F(1). In particular, PFS will be censored at the last adequate tumor assessment if one of the following occurs: absence of a PFS event; a PFS event occurs after a new anticancer therapy is given; a PFS event occurs after two or more missing tumor assessments. Discontinuation of study treatment (for any reason) will not be considered as a reason for censoring.

Kaplan-Meier estimates

The Kaplan-Meier (KM) estimate of the progression-free survival function will be computed for each treatment group. The results will also be plotted graphically (Kaplan-Meier curves) by

treatment and by randomization strata as assigned through IRT. The plots will display the number of subjects at risk at equidistant time points.

The estimated median PFS for each treatment group will be provided along with the approximate 90% confidence intervals (Brookmeyer and Crowley, 1982). Additionally, the 25th and 75th percentiles will also be computed. The log-log will be used to compute the confidence intervals.

Hazard ratio estimate

The hazard ratio estimate of a PFS event comparing the everolimus + exemestane combination therapy with placebo + everolimus, along with the two-sided 90% confidence interval, will be obtained from the stratified Cox proportional hazards model using the stratification information obtained through IRT. The model will include the indicator of assignment to the everolimus + exemestane arm or placebo + exemestane arm as the covariate. The baseline hazard function will be allowed to vary across strata. As this is an estimation based approach, no p-value will be provided.

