### **10.4.1 Variable**

The primary endpoint of this study is PFS, defined as the time from the date of randomization to the date of first documented progression or death due to any cause. A patient who has not progressed or died at the date of the analysis cut-off or receives another anticancer therapy will have their PFS censored at the time of the last adequate tumor evaluation before the earlier of the cut-off date or the anticancer therapy date. Disease progression for primary efficacy endpoint derivation will be assessed using the local (treating center's radiologist's) investigator's tumor assessment.

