**Table 14-5 Options for event dates used in PFS, TTP, duration of response**

Situation		Options for end-date (progression or censoring)  (1) = default unless specified differently in the protocol or RAP	Outcome
A	No baseline assessment	(1) Date of randomization/start of treatment 	Censored
B	Progression at or before next scheduled assessment	(1) Date of progression (2) Date of next scheduled assessment 	Progressed Progressed
C1	Progression or death after exactly one missing assessment	(1) Date of progression (or death) (2) Date of next scheduled assessment 	Progressed Progressed
C2	Progression or death after two or more missing assessments	(1) Date of last adequate assessment  (2) Date of next scheduled assessment  (3) Date of progression (or death)	Censored Progressed Progressed
D	No progression	(1) Date of last adequate assessment	Censored
E	Treatment discontinuation due to 'Disease progression' without documented progression, i.e. clinical progression based on investigator claim	(1) Ignore clinical progression and follow situations above (2) Date of discontinuation (visit date at which clinical progression was determined)	As per above situations Progressed
F	New anticancer therapy given	(1) Ignore the new anticancer therapy and follow situations above (ITT approach) (2) Date of last adequate assessment prior to new anticancer therapy (3) Date of secondary anti-cancer therapy (4) Date of secondary anti-cancer therapy	As per above situations Censored Censored Event
G	Deaths due to reason other than deterioration of 'Study indication'	(1) Date of last adequate assessment	Censored (only TTP and duration of response)

 =Definitions can be found in [Section 14.1.3.2.8](#).

 =After the last adequate tumor assessment. "Date of next scheduled assessment" is defined in [Section 14.1.3.2.8](#).

 =The rare exception to this is if the patient dies no later than the time of the second scheduled assessment as defined in the protocol in which case this is a PFS event at the date of death.

The primary analysis and the sensitivity analyses must be specified in the protocol. Clearly define if and why options (1) are not used for situations C, E and (if applicable) F.

Situations C (C1 and C2): Progression or death after one or more missing assessments: The primary analysis is usually using options (1) for situations C1 and C2, i.e.

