- (C1) taking the actual progression or death date, in the case of only one missing assessment.
- (C2) censoring at the date of the last adequate assessment, in the case of two or more consecutive missing assessments.

In the case of two or missing assessments (situation C2), option (3) may be considered jointly with option (1) in situation C1 as sensitivity analysis. A variant of this sensitivity analysis consists of backdating the date of event to the next scheduled assessment as proposed with option (2) in situations C1 and C2.

**Situation E: Treatment discontinuation due to ‘Disease progression’ without documented progression:** By default, option (1) is used for situation E as patients without documented PD should be followed for progression after discontinuation of treatment. However, option (2) may be used as sensitivity analysis. If progression is claimed based on clinical deterioration instead of tumor assessment by e.g. CT-scan, option (2) may be used for indications with high early progression rate or difficulties to assess the tumor due to clinical deterioration.

**Situation F: New cancer therapy given:** the handling of this situation must be specified in detail in the protocol. However, option (1) (ITT) is the recommended approach; events documented after the initiation of new cancer therapy will be considered for the primary analysis i.e. progressions and deaths documented after the initiation of new cancer therapy would be included as events. This will require continued follow-up for progression after the start of the new cancer therapy. In such cases, it is recommended that an additional sensitivity analysis be performed by censoring at last adequate assessment prior to initiation of new cancer therapy.

Option (2), i.e. censoring at last adequate assessment may be used as a sensitivity analysis. If a high censoring rate due to start of new cancer therapy is expected, a window of approximately 8 weeks performed after the start of new cancer therapy can be used to calculate the date of the event or censoring. This should be clearly specified in the analysis plan.

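### SAP 2.5.2 codes new anticancer therapy as F(1), count later events, while every written censoring rule for PFS is F(2), censor

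*SAP*

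**What the plan says.** SAP 2.5.2 adopts the default options of Table 14-5 for the final PFS analysis and lists them by code ("i.e. A(1), B(1), C1(1), C2(1), D(1), E(1), and F(1"). The sentence that follows, offered as an illustration of those codes, says PFS is censored if "a PFS event occurs after a new anticancer therapy is given".

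Table 14-5 gives several options for situation F, new anticancer therapy. The first is "1) Ignore the new anticancer therapy and follow situations above (ITT approach", and the second is "2) Date of last adequate assessment prior to new anticancer therapy", with outcome censored. The text on situation F in Appendix 1, section 14.1.3.2.10, says that under the first option "progressions and deaths documented after the initiation of new cancer therapy would be included as events", and that "option (1) (ITT) is the recommended approach". The table heading limits the status of the first options: "1) = default unless specified differently in the protocol or RAP".

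The protocol does specify differently. Under Protocol 10.4.1 a patient who "receives another anticancer therapy will have their PFS censored at the time of the last adequate tumor evaluation" before the earlier of the cut-off and the new therapy. Protocol 10.4.3, SAP 2.5.1 and SAP 2.5.3 state the same rule. SAP section 4 reports no departure from the protocol's analyses.

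**The concern.** The code list and the sentence after it give opposite outcomes for the same patient. Someone who stops study treatment, starts another anticancer drug and then progresses is an event under the code and is censored under the prose. Nothing in SAP 2.5.2 says which prevails.

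The code does not read as an obvious slip. The same paragraph invokes the intention-to-treat principle, Table 14-5 labels F(1) the ITT approach, and the appendix recommends it. SAP 2.4.8 sends the reader to Appendix 1 for the censoring rules after further therapy, and there F(1) is the default.

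The situation is foreseeable. Protocol 4.1 collects therapy given between end of treatment and progression, and does not list new therapy among the reasons to stop tumour assessments. Events after new therapy can therefore be in the database.

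If the code is programmed, the hazard ratio, medians and event count for the primary endpoint in the final report follow a rule the protocol did not specify, under a statement that nothing changed. SAP 2.5.4 plans no sensitivity analysis, so the final report would not show the difference.

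**Working it through.** **Statements side by side.** Each place that says what happens at new anticancer therapy:

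| Place | Rule | Table 14-5 option |
|---|---|---|
| SAP 2.5.2, code list | Ignore the therapy; later event counts | F(1) |
| SAP 2.5.2, next sentence | Censor | F(2) |
| SAP 2.5.1 | Censor at last adequate assessment before therapy | F(2) |
| SAP 2.5.3 | Same | F(2) |
| Protocol 10.4.1 | Same | F(2) |
| Protocol 10.4.3 | Same | F(2) |

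Five statements give F(2) and one gives F(1). The next sentence of SAP 2.5.2 does not itself say that the censoring scan must precede the therapy; SAP 2.5.1 and 2.5.3 supply that. Since the table lets the protocol or analysis plan override option (1), and Protocol 10.4 does so, F(1) is not the default for situation F in this trial.

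**Direction of the event count.** Hold C1(1) and C2(1) fixed, as the SAP does. An event counted under F(2) is a first progression or death that does not follow new therapy and does not follow two or more missing assessments. F(1) counts it too. F(1) also counts first events that follow new therapy, provided they do not follow two or more missing assessments. So events under F(1) are at least as many as under F(2), and the excess is exactly that second group. F(1) can also move censoring dates later in patients without an event, because scans after the new therapy would count.

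**Precision.** Inputs from Protocol 10.6: hazard ratio 0.62, 110 events, 1:1 allocation, 90% CI. With d events,

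SE(log HR) = 2/√d, and CI = 0.62 × exp(±1.645 × SE).

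At d = 110, SE = 2/√110 = 0.191 and the CI is 0.453 to 0.848, which reproduces the protocol's 0.45 to 0.85.

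The documents do not give the number of extra events under F(1). Assuming 5, 10 or 20 on top of 110:

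| Extra events (assumed) | d | SE | 90% CI |
|---|---|---|---|
| 0 | 110 | 0.191 | 0.453 to 0.848 |
| 5 | 115 | 0.187 | 0.456 to 0.843 |
| 10 | 120 | 0.183 | 0.459 to 0.837 |
| 20 | 130 | 0.175 | 0.465 to 0.827 |

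If 110 is instead read as the F(1) count and 20% of those events are assumed to fall after new therapy, F(2) leaves 110 × 0.8 = 88 events and a CI of 0.437 to 0.880. Both readings hold the hazard ratio at 0.62. They say nothing about a shift in the estimate itself, which would depend on how many patients in each arm start new therapy early and on their prognosis.

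**The case against.** The best reply is that this is a one-character slip that the documents already resolve. The censoring rule is written out five times in the same sense, once directly after the code, and SAP 2.5.3 gives a full derivation. The table subordinates its defaults to the protocol. The declaration of no change in SAP section 4 is true under the prose and so supports F(2). The scope is also narrow: this SAP serves the final report only, the primary PFS analysis was reported earlier at the 19 May 2020 cut-off, and there is no hypothesis test.

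Most of that stands, and it limits the seriousness. The intended rule can be recovered, the analysis affected is a descriptive update, and no material numerical effect has been shown. Collecting therapy before progression shows that situation F was foreseen but gives no frequency. The illustrative intervals use the planned event count for the primary analysis, not the unknown final count. The pointer in SAP 2.4.8 is not false in itself, since Appendix 1 contains F(2) and defers to the protocol.

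It does not remove the contradiction. The code list is an operative instruction for the primary endpoint, the sentence that contradicts it is presented as an instance of it, and a programmer needs one rule.

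**Conclusion.** The concern holds. F(1), and the description of situation F as a default, are wrong in SAP 2.5.2; the rule in Protocol 10.4 and in the rest of the SAP is F(2). This rests on the text alone.

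Only the direction of the event count is certain: F(1) gives the same number or more. The change in the hazard ratio and medians is unknown. The effect on interval width is small under the assumed counts, moving either limit by about 0.02 at most when up to 20 events are added to 110. The planned 110 events, 160 patients and stated CIs do not depend on the code. It should be corrected because it concerns the primary endpoint and the correction costs almost nothing.

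**What to change.** - In SAP 2.5.2, write the codes as A(1), B(1), C1(1), C2(1), D(1), E(1) and F(2). Describe the first six as Table 14-5 defaults and F(2) as the protocol's rule under 10.4.
- In SAP 2.4.8, refer to SAP 2.5.3 for censoring at new therapy instead of Appendix 1. This is secondary, but it removes a route back to F(1).
- If F(1) was in fact intended, the five censoring statements and SAP section 4 would have to change instead.

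The cost is two wording changes and no new data.

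Two additions are optional and not needed to cure the contradiction: a table row giving, by arm, the number censored for starting new anticancer therapy (a category already defined in Appendix 1, section 14.1.4.5.6), and one F(1) sensitivity run on the scans available. Together they add one row and one Cox and Kaplan-Meier output.
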